## **10.5 Secondary endpoints: NEW/SOFA Scores in adults, and PEW/PELOD Scores in children**

The NEW and SOFA Scores are evaluated in subjects of age  $\geq 18$  years, and the PEW and PELOD Scores are evaluated in subjects of age  $< 18$  years. The Scores are evaluated at Day 0, and Days 3 and 7.

Notes:

- If a subject has a missing Score at Day 0, the subject will be excluded from the analysis. If a subject has a missing Score at Day 3 (or at Day 7) for reason other than death, then the last available Score will be used instead.
- If a subject was on ECMO on Day 0, the subject will be excluded from the analysis as these scores are affected by the ECMO intervention.
- For a subject who dies without having a Score obtained at Day 3 (or at Day 7), then the Score and change in Score will be assumed to be (ie ranked) worse than any Score and change in Score for a subject who has a Score at Day 3 (or at Day 7).
- For a subject who starts ECMO during follow-up, then the Score and change in Score on those days when on ECMO will be assumed to be (ie ranked) worse than any Score and change in Score for a subject who has Score on that day (but ranked better than a subject who died before that day).

- a. Table: Completeness of evaluations for Score showing number (%) at each visit who:

- i. have all of the evaluations necessary to calculate the Score
- ii. have some but not all evaluations necessary to calculate the Score
- iii. died prior to the visit
- iv. were lost to follow-up prior to the visit
- v. were in follow-up but on ECMO
- vi. were in follow-up but have missing values for all of the evaluations necessary to calculate the Score.

b. Table: median, 25th and 75th percentiles, min and max Score at each of Days 0, 3 and 7, showing also number missing.

c. Table: median, 25th and 75th percentiles, min and max of change in Score at each of Days 3 and 7, showing also number missing. At each of Days 3 and 7: difference in medians between treatments, p-value from Wilcoxon's test and associated 95% CI for difference. Wei-Johnson Test will be used to provide a comparison between treatments combining over Days 3 and 7.

d. Sensitivity analysis: The sensitivity of the results to the handling of missing values at Days 3 and/or 7 (for reasons other than death) will be evaluated by considering the above analysis under more extreme scenarios than carrying forward the last available measurement: specifically by ranking subjects in one treatment group as having unfavorable changes (same rank as subjects who die) and subjects in the other treatment group as having favorable outcomes (equal to the best change); and vice versa.

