2.2 Secondary Objectives

1. Evaluate the efficacy and safety of treatment with high-titer versus low-titer anti-influenza immune plasma as an addition to standard care, using the following parameters:

- The ordinal primary outcome assessed at Days 1, 2, 3, 14, and 28
- Duration of initial hospitalization
- 28-day mortality
- In-hospital mortality during initial hospitalization
- Composite of mortality and hospitalization at Days 7, 14, and 28
- Change from baseline to Day 3 and Day 7 in NEW/PEW score
- Duration of supplemental oxygen use among those requiring oxygen at randomization
- Incidence of new oxygen use during the study
- Duration of ICU stay among those requiring ICU admission at randomization
- Incidence of new ICU admission during the study
- Duration of mechanical ventilation use among those requiring mechanical ventilation at randomization
- Incidence of new mechanical ventilation use during the study
- Duration and severity of ARDS among those meeting the definition of ARDS at randomization
- Incidence and severity of new ARDS during the study
- Duration of ECMO use among those requiring ECMO at randomization
- Incidence of new ECMO use during the study
- Change from baseline to Day 3 and Day 7 SOFA score for age \geq 18 years, and PELOD score for age $<$ 18 years
- Disposition (home, rehabilitation, chronic nursing facility, initial hospitalization ongoing at 28 days, died in hospital) following the initial hospitalization

- Percent of subjects with influenza virus detectable in OP sample at Day 3

2. Compare the plasma and control groups for HAI titers at Days 1, 3, and 7.

3. Evaluate the safety of high titer anti-influenza plasma as compared to low titer plasma as assessed by:

- Cumulative incidence of grade 3 and grade 4 adverse events (AEs)
- Cumulative incidence of serious adverse events (SAEs)

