12.2 Sample Size and Power Considerations

The planned sample size for the trial is 150 subjects, randomized in an approximately 2:1 ratio to high-titer versus low-titer anti-influenza plasma. To evaluate the power of the study, the following assumptions were made:

- a. The primary analysis will compare the high-titer and low-titer plasmas using a proportional odds model and a two-sided Type I error rate of 0.05.
- b. It is anticipated that very few of these subjects will be randomized and not start study plasma infusion (and so be excluded from the primary analysis) or be lost to follow-up prior to Day 7 (and so have missing data for the primary endpoint). In addition, power is reduced slightly and hence the effective sample size is reduced by interim analyses reviewed by the DSMB. Conservatively, a 10% reduction in the total sample size from 150 to 135 subjects was made to allow for these issues.
- c. Data from the control arm of IRC002 for adults with influenza A infection, NEW score ≥ 3 , and duration of time from onset of symptoms of influenza to randomization ≤ 6 days, suggests the distribution of subjects in the low-titer arm for the primary endpoint shown in the following table:

Table 12: Anticipated Distribution of Subjects in the Ordinal Scale

| | Low-Titer Arm | High-Titer Arm | |
|---|----------------------|-----------------------|-----------|
| | (Based on IRC 002) | 80% Power | 90% Power |
| Died | 10% | 4.3% | 3.7% |
| In ICU | 35% | 20.4% | 18.4% |
| Non-ICU hospitalization, requiring supplemental oxygen | 25% | 23.6% | 22.6% |
| Non-ICU hospitalization, not requiring supplemental oxygen | 10% | 13.3% | 13.4% |
| Not hospitalized, but unable to resume normal activities | 5% | 7.9% | 8.2% |
| Not hospitalized, but with full resumption of normal activities | 15% | 30.6% | 33.7% |
| Proportional odds ratio comparing high titer to low titer | | 2.50 | 2.88 |

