Based on the above assumptions, the table also shows the type of true difference (assuming proportional odds) that would be detected with 80% or 90% power. For example, the study would have 80% power to detect a proportional odds ratio of 2.50. This is the odds ratio that arises when comparing the proportion not hospitalized and able to resume normal activities in the high-titer arm (30.6%) to that in the low-titer arm (15%). The proportional odds model assumes that the same odds ratio applies to the cumulative proportions moving up the ordinal scale: for example, for the proportion not hospitalized in the high-titer arm ($30.6+7.9=38.5\%$) to that in the low-titer arm ($15+5=20\%$); or for the proportion alive and not in an ICU in the high-titer arm ($30.6+7.9+13.3+23.6=75.4\%$) to that in the low-titer arm ($15+5+10+25=55\%$).

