12.3 Statistical Analysis

A detailed statistical analysis plan will be developed before undertaking any comparative analyses of outcomes for the randomized high and low plasma titers. The following provides a brief summary of approach to analysis for the primary endpoint.

As noted above, the primary analysis will use a modified intention-to-treat approach which excludes randomized subjects who do not have an infusion of study plasma started. Statistical inferences will use a two-sided Type 1 error rate of 0.05, and corresponding 95% confidence intervals.

Analysis of the primary endpoint (ordinal outcome of clinical status at Day 7) will use a proportional odds model with an indicator variable for randomized treatment. It is useful to note that the score test of the treatment effect from a proportional odds model is equivalent to a Wilcoxon rank sum test even if the proportional odds assumption does not hold. If there are missing data for the primary endpoint, then sensitivity analyses will be undertaken to evaluate the sensitivity of study conclusions to the handling of the missing data. The proportional odds model will be extended to undertake comparisons of randomized treatments adjusted for variables that might be predictive of the outcome, for example, the ordinal clinical status at baseline. The model will also be extended to evaluate possible differences in the comparison of randomized treatments between subgroups of subjects (treatment by subgroup interaction), including subgroups defined by sex, age (adult/child), race/ethnicity, ordinal clinical status at baseline, NEW score at baseline, and days since onset of influenza symptoms to randomization.

Binary variables such as 28-day mortality, in-hospital mortality, incidence of new ICU admissions, etc., are expected to occur infrequently and will be compared between randomized arms using exact logistic regression. Quantitative variables such as duration of ICU stay and change from baseline in NEW score, etc., are expected to have reasonably skewed distributions and may be subject to censoring (e.g., for subjects in an ICU on Day 28); these will be compared between randomized arms using non-parametric tests (e.g., Wilcoxon's Test adapted, if necessary, to handle censoring).

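### The NEW/SOFA and PEW/PELOD comparisons test raw change without adjusting for the Day 0 Score: valid, but possibly inefficient, and the floor at 0 ranks some recovered survivors below still-ill ones

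*SAP*

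**What the plan says.** Protocol 2.2 lists "Change from baseline to Day 3 and Day 7 in NEW/PEW score" among the secondary parameters, and SOFA/PELOD likewise. Protocol 12.3 gives the reason for a rank test: "Quantitative variables such as duration of ICU stay and change from baseline in NEW score, etc., are expected to have reasonably skewed distributions".

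SAP 10.5 item c carries this out. It tabulates "min and max of change in Score at each of Days 3 and 7, showing also number missing", and at each day reports "difference in medians between treatments, p-value from Wilcoxon's test and associated 95% CI for difference". A Wei-Johnson test combines Days 3 and 7. No covariate and no stratum is named.

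The notes to SAP 10.5 exclude subjects who lack a Day 0 Score or were on ECMO at Day 0. They rank deaths worst, with subjects on ECMO next. Item d, the only sensitivity analysis there, concerns missing values.

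Elsewhere, SAP 10.1 specifies adjustment for baseline clinical status, for the primary endpoint. SAP 6 says only that imbalance may be examined in adjusted analyses. SAP 10.5 item b tabulates the actual Scores by day but does not test them.

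**The concern.** There are two separate issues.

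**Efficiency.** A change score uses the Day 0 Score with a coefficient fixed at 1. If the true regression of the follow-up Score on Day 0 has a slope below 1, subtraction leaves baseline noise in the comparison that an estimated coefficient would remove. The Day 0 Score is already collected and already required for inclusion in the analysis, so this precision is available at almost no cost.

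**Ordering.** The Scores have a floor of 0, so the largest possible improvement is the Day 0 Score itself. A subject who starts low and becomes entirely normal can show a smaller change than a subject who starts high and remains ill. The rank test then treats the first as the worse outcome.

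At stake is the sensitivity and the reading of a group of secondary endpoints. The primary result is not affected.

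**Working it through.** **Inputs from the documents.** From Protocol 12.3: "Statistical inferences will use a two-sided Type 1 error rate of 0.05, and corresponding 95% confidence intervals". From Protocol 12.2: subjects are "randomized in an approximately 2:1 ratio to high-titer versus low-titer anti-influenza plasma", and "a 10% reduction in the total sample size from 150 to 135 subjects was made to allow for these issues", which gives 90 v 45. The entry threshold is NEW or PEW of at least 3 (Protocol 4.2). The documents give no SD, correlation, effect or power for any of these Scores, so those are assumed below and shown over a range.

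**The plan's own figure.** The only stated power is for the primary endpoint: "the study would have 80% power to detect a proportional odds ratio of 2.50", with 90% at 2.88 in Table 12. Whitehead's formula is power = Φ(√V·ln OR − 1.96), with V = N·k/[3(k+1)²]·(1 − Σp̄³), k = 2, N = 135 and p̄ from Table 12. It gives about 81% and 90%, so the plan's figures reproduce.

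**Variance.** Let σ0 and σ1 be the Day 0 and follow-up SDs and ρ their correlation.

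- Var(change) = σ0² + σ1² − 2ρσ0σ1
- Var(adjusted) = σ1²(1 − ρ²)
- Difference = (σ0 − ρσ1)², which is never negative, and is zero only when the slope ρσ1/σ0 equals 1.

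With equal SDs, Var(adjusted)/Var(change) = (1+ρ)/2. With σ1 = 1.3σ0, it is 1.69(1 − ρ²)/(2.69 − 2.6ρ). Suppose the adjusted analysis has 80% power (noncentrality 1.96 + 0.84 = 2.80). The change analysis then has power Φ(2.80·√ratio − 1.96).

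| ρ | Ratio, equal SDs | Worth, of 135 | Power of change | Ratio, σ1 = 1.3σ0 | Power of change |
|---|---|---|---|---|---|
| 0.3 | 0.65 | 88 | 62% | 1.538/1.91 = 0.81 | 71% |
| 0.5 | 0.75 | 101 | 68% | 1.268/1.39 = 0.91 | 76% |
| 0.7 | 0.85 | 115 | 73% | 0.862/0.87 = 0.99 | 80% |
| 0.9 | 0.95 | 128 | 78% | not calculated | not calculated |

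The variance ratios do not depend on sample size. Absolute power for the adult Scores would be lower than with all 135. If children are as frequent as in IRC002 (11 of 98, Protocol 1.2.2.4), there are about 150 × 11/98 ≈ 17 of 150. That leaves about 133 adults, or 120 (80 v 40) after the same 10% reduction.

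**Rank tests on floored integer scores.** A simulation used 3,000 trials per setting, 90 v 45, Day 0 Scores centred on 7 with SD 3 and restricted to 3 or more, follow-up centred on 4 with SD 3 and floored at 0, and a 1.5-point effect. All of these are assumptions. It compared the Wilcoxon test on change with a rank ANCOVA of the follow-up Score on Day 0, deaths being ranked worst in both.

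| ρ (before truncation and floor) | No deaths: change v adjusted | About 5% deaths: change v adjusted |
|---|---|---|
| 0.3 | 56% v 80% | 55% v 74% |
| 0.5 | 70% v 85% | 69% v 81% |
| 0.7 | 90% v 94% | 84% v 90% |
| 0.85 | 99% v 100% | 98% v 98% |

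Type I error was 4.8% to 5.7% for the planned test and 5.0% to 6.2% for rank ANCOVA. The 6.2% came at ρ = 0.3 with deaths, so a small part of the gain in that setting may reflect it. A second simulation at 80 v 40 with 5% deaths gave 45% v 61%, 57% v 68% and 78% v 80% at ρ = 0.3, 0.5 and 0.7. The direction is the same and the gain at 0.7 is small.

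**Ordering.** NEW 3 to 0 is a change of −3; NEW 12 to 8 is −4. The second ranks as the better outcome, although 8 is well above the entry threshold of 3. In the first simulation, 11% to 25% of pairs made up of one recovered survivor (Score 0) and one still-ill survivor (Score 3 or more) were reversed in this way. That percentage depends on the assumed Score distributions; the existence of the reversal does not.

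**The case against.** The strongest reply is that the planned analysis does what the protocol set out to do. The objective is change from baseline, Protocol 12.3 plans non-parametric tests for it, and the SAP follows. A change endpoint measures how much a subject improved rather than where the subject ended, so the 3-to-0 example describes the chosen endpoint and affects both arms alike. End state is covered elsewhere: SAP 10.1 and 10.2 test the ordinal scale on each study day, and 10.5 item b shows the actual Scores. Deaths and days on ECMO already rank worst, so reversals are confined to observed Scores. All of this stands. It makes the point one of efficiency and interpretation. It does not supply a Day 0 adjustment or a test of the Scores themselves, which Protocol 12.4.2 lists as endpoints.

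The objection on size is also sound. Nothing in the documents fixes the correlation or the SDs. The entry threshold narrows the spread at Day 0, while IRC002 subjects were widely dispersed by Day 7, so a larger follow-up SD is plausible and would shrink the gain while the slope stays below 1. Carrying the last Score forward would tend to raise the correlation, with the same effect.

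A reader might infer that the analysis ignores the Day 0 Score. It does not: change subtracts that Score, and subjects without one are excluded. What is missing is an estimated coefficient.

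**Conclusion.** The point holds as a modest weakness in secondary analyses. The tests in SAP 10.5 item c are unadjusted tests of raw change. Under normal theory they cannot be more efficient than a Day 0-adjusted comparison. The floor also makes some recovered survivors rank below still-ill ones.

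The size is uncertain. With equal SDs the adjusted variance is 35%, 25% and 15% smaller at ρ = 0.3, 0.5 and 0.7. With a follow-up SD 1.3 times the Day 0 SD, it is about 19%, 9% and 1% smaller. The gain is negligible as the slope on Day 0 approaches 1. These figures rest on assumed correlations, SD ratios and, for the simulations, Score distributions and effect.

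Two stronger readings are not supported. One is that the planned test is invalid or biased: under randomization it keeps its error rate (about 5% in simulation), and it agrees with the protocol. The other is that adjustment would uncover an effect hidden in subjects with low Day 0 Scores: a main-effect covariate estimates one common treatment effect and does not target that group.

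**What to change.** In SAP 10.5 item c, add for the adult Scores (NEW and SOFA) a comparison of the Day 3 and the Day 7 Score between arms, adjusted for the Day 0 Score. Use rank ANCOVA or a proportional odds model, chosen in advance, and keep the existing worst ranks for death and ECMO. Ranking the follow-up Score orders subjects by end state, which removes the reversal from this comparison.

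Keep the Wilcoxon and Wei-Johnson tests on change, and the item d sensitivity analysis, as they are written.

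For PEW and PELOD, use only the rank-based version, or leave the comparison descriptive if few children enrol. With about 17 children (roughly 11 v 6), a proportional odds model with a covariate would be fragile.

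The cost is SAP wording and slightly more analysis; no new data are needed. The drawback is a second p-value for each Score and day, so the SAP should say, before any comparative analysis, which comparison is the main one and which is supportive.

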#### **10.6 Secondary endpoint: Detectable influenza virus in OP sample at Day 3**

a. Table: Number (%) with positive result at Day 3, number not evaluated by reason (death, prior loss to follow-up, in follow-up but no result), difference in %'s between treatments, and odds ratio comparing treatments with p-value and associated 95% CI from exact logistic regression.

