6.3.3.2.1 Pediatric Blood Collection Guidelines

Refer to institutional policies and recommendations on safe blood sample volume limits for pediatric patients. Sites may reduce the volume of research blood sample collection in order to remain within these limits.

6.3.3.3 Baseline Research Procedures on Day 0

The following baseline research procedures will be performed after screening evaluations and determination of eligibility have been completed but prior to randomization and plasma administration. These must be performed just prior to randomization (no more than 4 hours between collection and randomization). Baseline research samples should not be collected for screen failures.

- OP (throat) swab for quantitative PCR
- 25.5 mL of blood for adults or 8.5 mL of blood for children should be obtained. This will be used for the following laboratory tests:
 - HAI to influenza A/H1N1 and A/H3N2
 - Stored samples for other research tests evaluating the immune response to influenza as defined in Section [7.5](#)

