7.2 Influenza A Diagnostics - Viral Shedding

OP swabs will be processed to determine quantitative PCR for influenza A.

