12.4.2 Secondary Endpoints

- Ordinal outcome assessed at Days 1, 2, 3, 7, 14, and 28
- Date of hospital admission and discharge
- Date and cause of death (if applicable)
- NEW/PEW score at Day 0, 3, and 7
- Date/time of supplemental oxygen initiation and discontinuation (if applicable)
- Date/time of ICU admission and discharge (if applicable)
- Date/time of mechanical ventilation initiation and discontinuation (if applicable)
- Date/time of meeting ARDS criteria, date of resolution, and severity (if applicable)
- Date/time of ECMO initiation and discontinuation (if applicable)
- SOFA score for age \geq 18 years and PELOD score for age $<$ 18 years on Days 0, 3, and 7
- Disposition (home, rehabilitation, chronic nursing facility) following the initial hospitalization
- Quantitative PCR for influenza in oral swab on Day 0 and 3.
- Grade 3 and 4 adverse events
- SAEs
- Safety laboratory tests will be collected on Days 0, 1, 3, and 7
- CBC with differential white cell count (to include neutrophil and lymphocyte percentages), hemoglobin, hematocrit, and platelets
- Blood chemistries (creatinine, glucose, total protein, ALT/GPT, AST/GOT, total bilirubin)
 - Hemagglutination Inhibition (HAI) titer Days 0, 1, 3, 7
 - Grade 3 and grade 4 adverse events (AEs)
 - Serious adverse events (SAEs)

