## 6. Baseline characteristics (mITT population)

Baseline characteristics are those recorded as Day 0; if values are missing but are available from screening assessments, then these will be used instead. Tables in this section will show number (%) for categorical variables, and median, 25th and 75th percentiles, min and max for the ordinal/continuous variables; number with missing values. No statistical comparison will be undertaken between randomized arms (instead, the impact of any imbalance may be evaluated in adjusted analyses—see efficacy analyses section).

- a. Table: Number randomized: overall and by month/influenza season (generally November – March, but for grouping will be August – July). Dates of first and last randomizations.
- b. Table: Number randomized by site.
- c. Table of demographic characteristics: Age at randomization and associated age group (adult versus child, with children classified as <2 years, ≥2 to <8 years, and ≥8 to <18 years); sex;

pregnancy status; self-reported NIH race/ethnicity (major category race, minor category ethnicity).

- d. Table of body mass index (BMI) and BMI group (adults only, using standard U.S. categories for underweight, etc.).
- e. Table of influenza disease status: Influenza vaccination in the current season; days from onset of influenza symptoms to randomization; influenza antivirals taken through to randomization (number (%)) for each specific drug or combination of drugs, and number (%) taking any antivirals); influenza status by site testing (negative versus positive, type of testing), influenza status from central lab from Day 0 (negative versus positive) and subtype from central laboratory testing; viral shedding in OP sample by qPCR at central laboratory testing.
- f. Table of days hospitalized prior to randomization
- g. Table of chronic medical conditions and allergies (defined as starting >30 days prior to randomization), by MedDRA SOC and PT.
- h. Table of vital signs, including SaO2.
- i. Table of clinical status: Study 6-point ordinal scale; measures of clinical support (hospitalization, oxygen requirement, mechanical ventilator requirement, ICU requirement, ECMO requirement), ARDS (yes/no, and by severity)
- j. Table of respiratory status: PaO2/ FiO2 Ratio, SpO2/ FiO2 Ratio [excluding those on ECMO as these criteria are erroneous in this population].

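### SAP 10.6 validly answers the Day 3 percent-detectable objective, but its treatment comparison leaves out the quantitative PCR result and the Day 0 swab and so loses precision

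*SAP*

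**What the plan says.** The protocol collects a quantity on both days. Section 7.2 states that "OP swabs will be processed to determine quantitative PCR for influenza A". Section 6.3.3.3 schedules the baseline swab ("OP (throat) swab for quantitative PCR") just before randomization, and 6.3.7.3 repeats it on Day 3. Section 12.4.2 lists "Quantitative PCR for influenza in oral swab on Day 0 and 3" under secondary endpoints.

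The worded secondary objective in protocol 2.2, repeated in the SAP's protocol summary, is narrower: "Percent of subjects with influenza virus detectable in OP sample at Day 3".

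SAP 10.6 follows that objective. It tabulates "Number (%) with positive result at Day 3", counts those not evaluated by reason, and gives a difference in percentages and an "odds ratio comparing treatments with p-value and associated 95% CI from exact logistic regression". It has no Day 0 covariate, no restriction to subjects positive at Day 0, and no analysis of load or change in load. The Day 0 quantitative result appears only in the descriptive baseline table of SAP section 6, item e, as "viral shedding in OP sample by qPCR at central laboratory testing".

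**The concern.** Reducing a measured viral load to detected or not detected discards information, and so does ignoring a baseline value of the same quantity. The SAP uses baseline elsewhere: 10.5 analyses change from Day 0 for the NEW, SOFA, PEW and PELOD scores, and 10.1 adds a model for the primary endpoint adjusted for baseline clinical status.

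Baseline is likely to vary here. Under protocol 4.2 and 6.3.1.5 a subject can qualify on a local test of a nasal, throat, sputum or other respiratory specimen up to 48 hours old, with illness onset up to 6 days earlier. Some subjects may therefore be negative on the Day 0 throat swab, and SAP section 6 item e already plans to tabulate central-laboratory Day 0 status as negative or positive. Those subjects add noise to a Day 3 detected/not-detected comparison.

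At stake is how much the planned treatment comparison of virus can show. Protocol 1.3.1 chose low-titer plasma as control partly to test whether anti-influenza antibody is the active component. The HAI analyses show antibody exposure; this endpoint is the planned comparison of effect on the virus. A null result from an inefficient test would be hard to interpret.

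**Working it through.** **1. Inputs from the documents.** Allocation is 2:1, and protocol 12.2 reduces 150 subjects to 135 effective, so 90 v 45. The design is set "using a proportional odds model and a two-sided Type I error rate of 0.05". No power, detection rate or effect size is stated for the virologic endpoint.

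**2. The plan's own power figure, reproduced first.** This is for the primary endpoint. With A = 2 and the Table 12 control distribution,

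N = 3(A+1)²(z_α + z_β)² / [A (ln OR)² (1 − Σp̄³)].

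For OR 2.50: 27 × 7.849 / (2 × 0.8396 × 0.951) ≈ 132.7, which is 80.7% power at 135. For OR 2.88, N ≈ 133.4 and power at 135 is 90.3%. The stated 80% and 90% are sound, and nothing below affects them.

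**3. Large-sample efficiency of the binary outcome.** Relative to an uncensored normal outcome, a split with detection proportion p has efficiency φ(z_p)² / [p(1−p)]. Adjusting the continuous analysis for a baseline with correlation ρ multiplies this by (1−ρ²).
- p = 0.5: 0.3989² / 0.25 = 0.64; with ρ = 0.5, 0.64 × 0.75 = 0.48.
- p = 0.8: 0.2800² / 0.16 = 0.49; with ρ = 0.5, 0.49 × 0.75 = 0.37.

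These overstate the loss, because real load data are cut off at the detection limit.

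**4. Simulation that allows for undetectable values.** Setup: 90 v 45, 3,000 runs per row. Assumed, not in the documents: a true shift of 0.5 SD in log load, 90% detection on Day 0, and the detection rates and correlations shown. Fisher's exact test stands in for unadjusted exact logistic regression. Undetectable values are tied lowest. Entries are power in percent.

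| Control detection, Day 3 | ρ | Exact binary (plan) | Wilcoxon, Day 3 load | Rank ANCOVA with Day 0 | Gain over plan, points |
|---|---|---|---|---|---|
| 40% | 0 | 51.2 | 60.2 | 60.3 | 9 |
| 40% | 0.5 | 50.4 | 60.8 | 66.1 | 16 |
| 40% | 0.7 | 50.7 | 60.7 | 74.9 | 24 |
| 60% | 0 | 55.6 | 67.8 | 67.7 | 12 |
| 60% | 0.5 | 57.7 | 69.0 | 76.9 | 19 |
| 60% | 0.7 | 57.2 | 69.0 | 87.2 | 30 |
| 80% | 0 | 49.5 | 73.3 | 73.1 | 24 |
| 80% | 0.5 | 48.4 | 74.2 | 82.6 | 34 |
| 80% | 0.7 | 47.0 | 74.3 | 92.8 | 46 |

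Implied efficiency is [(z_power,plan + 1.96) / (z_power,alternative + 1.96)]². In the first row this is (1.99/2.22)² ≈ 0.80; in the last, (1.88/3.42)² ≈ 0.30.

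**5. How much is test size.** Under no effect, Fisher's test rejects 3.4% to 4.5% of the time, against 4.4% to 5.6% for rank ANCOVA. A chi-square test, whose size is near 5%, has 57.1% power in the first row and 50.7% in the last. Against it the gains are about 3 and 42 points. In the mildest case, most of the 9 points therefore comes from the conservatism of the exact test.

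**6. Less favourable settings.** A second simulation used 400 runs, 85 v 42 subjects, SD 1.8 log10 and a detection limit of 2 log10, and compared Fisher's test with baseline-adjusted left-censored regression.
- Effect 0.8 log10, 33% control detection, ρ = 0.2: 39% v 44%.
- Effect 0.8 log10, 71% control detection, ρ = 0.5: 42% v 70%.
- Effect 0.3 log10, up to 71% detection and ρ = 0.5: no power above about 16% by either method.

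**The case against.** The strongest reply is that SAP 10.6 delivers exactly the objective the protocol words. A reader might infer that the SAP dropped a prespecified endpoint, but the documents do not support that. Protocol 12.4.2 reads largely as a list of data items (dates of admission, safety laboratory tests), and quantitative PCR can be read there as the measurement behind the percent-detectable endpoint. The SAP introduction limits its scope to the major comparisons, including those needed for the objectives. Protocol 12.3 does assign quantitative variables to non-parametric tests, but does not name PCR. What remains is a gap in analysis rather than a departure from the objective.

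A reader might also infer bias, because subjects negative on Day 0 count as not detected on Day 3 without having cleared anything. Randomization makes the unadjusted comparison valid, and Day 0 shedding is tabulated by arm, so an imbalance would be visible. Only precision is at issue.

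The size of the loss is also open to challenge, and this stands. Every virologic parameter is assumed, part of the gap is the exact test's conservatism, and normal data suit censored regression. Protocol 1.2.2.4 reports no benefit in viral shedding in the predecessor plasma trial, so the true effect may be small. The viral-load effect cited in protocol 1.2.2.3 was for hyperimmune IVIG on Days 5 and 7, not for plasma on Day 3.

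**Conclusion.** The point holds as a matter of precision on a secondary endpoint. SAP 10.6 is valid and on objective, but it provides no treatment comparison of the quantitative PCR listed in protocol 12.4.2 and makes no use of the Day 0 swab in the comparison it does provide.

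For effects of roughly 0.4 to 0.5 SD (0.8/1.8 = 0.44 SD in the second simulation), the power given up ranges from about 5 to 9 points, with low Day 3 detection and weak correlation, to about 46 points, with 80% detection and correlation 0.7. A loss appeared in every setting with an effect of that size, but where the trial falls in the range cannot be read from the documents. If the true effect is small, neither analysis has much power and the absolute loss is small. A claim that most of the virologic information is lost would need high Day 3 detection and strong correlation, neither of which is documented. The primary analysis, its power and the sample size are unaffected.

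**What to change.** Keep the percent-positive table in SAP 10.6 and its unadjusted exact analysis as the answer to the stated objective.

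Before unblinding, add one supplementary comparison: Day 3 oropharyngeal log10 viral load between arms, adjusted for Day 0 load. Use either a rank-based ANCOVA with undetectable values tied lowest, in line with the non-parametric approach of protocol 12.3, or a regression left-censored at the detection limit. Name one as the main version. State rules for undetectable or missing Day 0 values and for deaths before Day 3; SAP 10.5 already ranks deaths worst for the clinical scores and could serve as a model.

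If the binary model is also to be adjusted, put Day 0 positive/negative into the exact model, or use ordinary logistic regression for continuous load. Exact conditioning on a continuous covariate generally leaves a degenerate distribution. Either adjustment makes the odds ratio conditional on baseline rather than marginal, and the SAP should say so.

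The cost is some SAP text, modest programming and one more supplementary analysis, plus a distributional assumption if censored regression is chosen. No new data are needed.
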